### **8.3.2 Time period and frequency for collecting AE and SAE information**

All AEs and SAEs will be collected from the signing of the ICF until the follow-up visit at the time points specified in the SoA ([Section 1.3](#)), or up to recovery or stabilization of any AE to be followed-up as specified in this protocol, whichever comes last.

All SAEs and AESI will be recorded and reported to the Sponsor or designee within 24 hours, as indicated in Appendix 3 ([Section 10.3](#)). The Investigator will submit any updated SAE data to the Sponsor within 24 hours of it being available.

Investigators are not obligated to actively seek AE or SAE after conclusion of the study participation. However, if the Investigator learns of any SAE, including a death, at any time after a participant has been discharged from the study, and he/she considers the event to be reasonably related to the study intervention or study participation, the Investigator must promptly notify the Sponsor.

The method of recording, evaluating, and assessing causality of AE and SAE and the procedures for completing and transmitting SAE reports are provided in Appendix 3 ([Section 10.3](#)).

### **8.3.3 Method of detecting AEs and SAEs**

Care will be taken not to introduce bias when detecting AEs and/or SAEs. Open-ended and non-leading verbal questioning of the participant is the preferred method to inquire about AE occurrences.

### **8.3.4 Follow-up of AEs and SAEs**

After the initial AE/SAE report, the Investigator is required to proactively follow each participant at subsequent visits/contacts. At the pre-specified study end-date, all SAEs, and non-serious AEs of special interest (as defined in [Section 8.3.1](#)), will be followed until resolution, stabilization, the event is otherwise explained, or the participant is lost to follow-up (as defined in [Section 7.3](#)). Further information on follow-up procedures is given in Appendix 3 ([Section 10.3](#)).

### **8.3.5 Regulatory reporting requirements for SAEs**

- Prompt notification by the Investigator to the Sponsor of a SAE is essential so that legal obligations and ethical responsibilities towards the safety of participants and the safety of a study intervention under clinical investigation are met.
- The Sponsor has a legal responsibility to notify both the local regulatory authority and other regulatory agencies about the safety of a study intervention under clinical investigation. The Sponsor will comply with country-specific regulatory requirements relating to safety reporting to the regulatory authority, Institutional Review Boards (IRB)/Independent Ethics Committees (IEC), and Investigators.
- Investigator safety reports must be prepared for suspected unexpected serious adverse reactions (SUSAR) according to local regulatory requirements and Sponsor policy and forwarded to Investigators as necessary.

- An Investigator who receives an Investigator safety report describing a SAE or other specific safety information (eg, summary or listing of SAEs) from the Sponsor will review and then file it along with the Investigator's Brochure and will notify the IRB/IEC, if appropriate according to local requirements.

### **8.3.6 Pregnancy**

See AESI ([Section 8.3.1](#)).

### **8.3.7 Adjudication Committee**

Adjudication will be performed by experts independent of sponsor for the evaluation of whether deaths, cardiovascular SAEs and respiratory SAEs meet criteria for certain safety endpoints. A confirmatory adjudication will occur for AECOPD exacerbations. Adjudicators will adjudicate these events in a consistent and unbiased manner throughout the study.

The goal of the adjudication is to ensure that all events reported by the site are judged uniformly, using pre-specified criteria by a group independent of the Sponsor. Adjudication Committee members will be blinded to treatment allocation. Adjudication Committee members' responsibilities and the process for data review are described in the AC Charter/Manual of Operation.

### **8.3.8 Disease-related events and/or disease-related outcomes not qualifying as AEs or SAEs**

In this study, some AEs are considered related to the underlying condition and thus will not be considered unexpected. Specifically, for patients with COPD worsening of underlying condition is not considered an AE unless it meets serious criteria as defined in Appendix 3 ([Section 10.3](#)).

Any other AE not listed as an expected event in the IB or in this protocol will be considered unexpected.

### **8.3.9 Guidelines for reporting product complaints / medical device incidents (including malfunctions)**

Any defect in the IMP/NIMP must be reported as soon as possible by the Investigator to the monitoring team that will complete a product complaint form within required timelines.

Appropriate information (eg, samples, labels or documents like pictures or photocopies) related to product identification and to the potential deficiencies may need to be gathered. The Investigator will assess whether or not the quality issue has to be reported together with an AE or SAE.

## **8.4 TREATMENT OF OVERDOSE**

Overdose is an AESI (defined in [Section 8.3.1](#)). No antidote is available for dupilumab.

In the event of an overdose, the Investigator/treating physician should:

1. Contact the Medical Monitor immediately.
2. Closely monitor the participant for any AE/SAE and laboratory abnormalities until study intervention can no longer be detected systemically.
3. Obtain a serum sample for PK analysis as soon as possible from the date of the last dose of study intervention if requested by the Medical Monitor (determined on a case-by-case basis).
4. Document the quantity of the excess dose as well as the duration of the overdose in the CRF.

Decisions regarding dose interruptions or modifications will be made by the Investigator in consultation with the Medical Monitor based on the clinical evaluation of the participant.

## 8.5 PHARMACOKINETICS

### 8.5.1 Systemic drug concentration and anti-drug antibodies

#### 8.5.1.1 Sampling time

Blood samples will be collected for determination of functional dupilumab and anti-dupilumab antibodies in serum as specified in the SoA ([Section 1.3](#)). Special procedures for collection, storage, and shipping of serum are described in separate operational manuals. The date and time of collection should be recorded in the patient e-CRF.

#### 8.5.1.2 Handling procedures

Special procedures for collection, storage, and shipping of serum are described in separate operational manuals. An overview of handling procedure for samples used in the determination of systemic drug concentration and ADA is provided in [Table 6](#).

**Table 6 - Summary of handling procedures for dupilumab**

Sample type	Functional dupilumab	Anti-dupilumab antibody
Matrix	Serum	Serum
Blood sample volume	5 mL	5 mL
Anticoagulant	None	None
Blood handling procedures	See Operational Manual	See Operational Manual
Serum aliquot split	2 aliquots	2 aliquots
Storage conditions	<6 months: below -20°C <24 months: below -80°C (preferred)	<6 months: below -20°C <24 months: below -80°C (preferred)
Serum shipment condition	In dry ice	In dry ice

### 8.5.1.3 *Bioanalytic method*

Serum PK and ADA samples will be assayed using validated methods as described in [Table 7](#).

**Table 7 - Summary of bioanalytical methods for dupilumab and anti-dupilumab antibodies**

Analyte	Functional dupilumab	Anti-dupilumab antibody
Matrix	Serum	Serum
Analytical technique	ELISA	Electro-chemiluminescence
Site of bioanalysis	Regeneron	Regeneron

ELISA=enzyme-linked immunosorbent assay.

Drug concentration information that may unblind the study will not be reported to investigative sites or blinded personnel until the study has been unblinded.

Note: If an SAE or any AESI of anaphylactic reactions or systemic allergic reactions that are related to IMP and require treatment, or severe injection site reactions lasting longer than 24 hours, occurs in a patient, blood samples should be collected for determination of functional dupilumab concentration, and ADA assessment at or near the onset and completion of the occurrence of the event, if possible. The exact date and time of sample collection must be recorded and entered into the database by the central laboratory. An unscheduled systemic drug concentration page in the eCRF must be completed as well. If necessary for safety monitoring, additional ADA samples may be collected after the EOS Visit until resolution of AE.

Specifically for PK, any changes in the timing or addition of time points for any planned study assessments must be documented and approved by the relevant study team member and then archived in the Sponsor and site study files, but will not constitute a protocol amendment. The IRB/IEC will be informed of any safety issues that require alteration of the safety monitoring scheme or amendment of the ICF.

## 8.6 PHARMACODYNAMICS

### 8.6.1 Pharmacodynamic variables/biomarkers

- Pharmacodynamic response of selected biomarkers
  - PARC
  - Eotaxin-3
  - FeNO (postbronchodilator)
  - Total IgE
  - Fibrinogen
- Serum/plasma for archival purposes
- Induced sputum for RNA expression (optional for patients at a subset of sites).

For timing of PD sample collection refer to SoA ([Section 1.3](#))

Assay methodologies are briefly summarized below. More detailed information on the collection, handling, transport, and preservation of samples (eg, minimum volumes required for blood collection and for aliquots for each biomarker assay) will be provided in a separate laboratory manual.

Specific procedures for collection, storage and shipping of samples collected for pharmacodynamics will be provided in a lab manual.

### **Whole blood biomarkers**

Blood eosinophil and neutrophil counts will be measured as part of the standard 5-part WBC differential cell count on a hematology auto analyzer. Blood eosinophil and neutrophil counts will be measured at timepoints additional to hematology ([Section 1.3](#)).

### **Plasma/serum biomarkers**

PARC will be assayed using a validated enzyme immunoassay.

Fibrinogen assay: (development of immunoassay method ongoing).

Eotaxin-3 will be measured in heparinized plasma with a validated enzyme immunoassay.

Total IgE will be measured with a quantitative method (eg, Phadia ImmunoCAP) approved for diagnostic testing.

### **Exhaled nitric oxide**

FeNO will be analyzed using a NIOX instrument (Aerocrine AB, Solna, Sweden), or similar analyzer using a flow rate of 50 mL/s, and reported in parts per billion (ppb). This assessment should be conducted prior to spirometry and following a fast of at least 1 hour. Further details on the procedure for measuring exhaled nitric oxide with NIOX will be provided in a separate instruction manual.

## **8.7 PHARMACOGENOMICS**

Pharmacogenetic/Pharmacogenomic testing is optional and voluntary. Written informed consent must be obtained before sampling.

For those patients who consent to the optional pharmacogenetic/pharmacogenomic sample collection section of the informed consent form (ICF), blood samples for exploratory genetic analysis of DNA or RNA will be collected at the study visit as specified in the SoA ([Section 1.3](#)), and these samples will be stored for future analysis. Specific procedures for collection, storage and shipping of pharmacogenetic/pharmacogenomic samples will be provided in a lab manual.

For patient(s) who have consented to it, the samples that are archived, unused or left over after planned testing may be used for additional research purposes (Appendix 17: Future use of samples, see [Section 10.17](#)).

In the event of DNA extraction failure, a replacement genetic blood sample may be requested from the participant.

## **8.8 BIOMARKERS**

Pharmacodynamic and pharmacogenetics biomarkers are described in [Section 8.6.1](#) and [Section 8.7](#), respectively.

## **8.9 HEALTH CARE RESOURCE UTILIZATION**

A questionnaire of health care resource utilization (reliever medication, physician visit, hospitalization, emergency or urgent medical care facility visit, sick leaves including loss of usual activity days) will be collected by the investigator for all participants throughout the study.

## 9 STATISTICAL CONSIDERATIONS

### 9.1 STATISTICAL HYPOTHESES

The primary analyses of the study compare the treatment effect of dupilumab 300 mg q2w against placebo on two primary endpoints.

The statistical hypotheses used to test dupilumab 300 mg q2w against placebo on reducing the annualized rate of moderate-to-severe COPD exacerbations over the 52-week treatment period are as follows:

- Null hypothesis:  $r_{dupilumab} / r_{placebo} = 1$
- Alternative hypothesis:  $r_{dupilumab} / r_{placebo} \neq 1$

Where  $r_{dupilumab}$  and  $r_{placebo}$  represent exacerbation rate in the dupilumab and placebo groups, respectively.

The statistical hypotheses used to test dupilumab 300 mg q2w against placebo on improving pre-bronchodilator FEV1 from baseline to Week 12 are as follows:

- Null hypothesis:  $c_{dupilumab} = c_{placebo}$
- Alternative hypothesis:  $c_{dupilumab} \neq c_{placebo}$

Where  $c_{dupilumab}$  and  $c_{placebo}$  represent change in pre-bronchodilator FEV1 in the dupilumab and placebo groups, respectively.

The statistical hypotheses to be tested on the key secondary endpoints, change in pre-bronchodilator FEV1 from baseline to Week 52 and change from baseline to Week 52 in the SGRQ total score compared to placebo, can be specified similarly as those on the change in FEV1 at Week 12. For the proportion of patients with SGRQ improvement  $\geq 4$  points at Week 52, the null hypothesis is the odds ratio of response between the dupilumab and placebo group is equal to 1, while the alternative hypothesis is the odds ratio is unequal to 1.

### 9.2 SAMPLE SIZE DETERMINATION

The sample size of the study is determined based on power calculations for the primary endpoints.

For the endpoint of annualized rate of moderate or severe COPD exacerbations over the 52-week treatment period, assuming the number of exacerbations following a negative binomial distribution with a dispersion parameter of 1, a placebo annualized rate of exacerbations being 1.5, an average treatment duration of 0.95 year (to account for an average of 5% of the planned treatment period with missing data), and a randomization ratio of 1:1 to the two treatment arms, with 924 randomized patients (462 for each treatment arm), the study will have 90% power to detect a 25% relative risk reduction (ie, annualized rate of 1.125 for the dupilumab group) in the annualized rate of moderate or severe COPD exacerbations at the 2-tailed significance level of  $\alpha=0.049$  (an administrative penalty of 0.001 will be taken from the significance level used at final analysis due to a planned interim analysis; details are provided in [Section 9.5](#)). For the endpoint of change from baseline in FEV1 at Week 12, the study will have 99% power to detect a 0.1L improvement at the significance level of  $\alpha=0.049$ , assuming a common standard deviation of 0.35 and 5% of patients with missing data.

Patients will be randomized using a 1:1 randomization ratio to dupilumab 300 mg q2w or placebo. Randomization will be stratified by country and asthma history (Yes or No).

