### **Number of participants:**

Approximately 924 patients are planned to be randomly assigned to study intervention for an estimated total of 462 evaluable patients per intervention group (see [Section 9.2](#)).

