#### 9.4.1.1 **Multiplicity considerations**

Multiplicity is considered for testing multiple endpoints. The overall type-I error rate will be controlled at the two-sided 0.05 level.

An IA is planned in this study (details are provided in [Section 9.5](#)), and an administrative penalty of 0.001 will be taken from the significance level used at final analysis and thus two-sided 0.049 will be used. A sequential testing procedure will be used for testing the two primary endpoints in the following order:

- E 01. Annualized rate of moderate and severe COPD exacerbations over 52 week treatment period
- E 02. Change in pre-bronchodilator FEV1 from baseline to Week 12

The annualized rate of moderate and severe COPD exacerbations over the 52 week treatment period will be first tested at the two-sided 0.049 significance level. Only upon rejection of the null hypothesis for the annualized rate of moderate and severe COPD exacerbations can the change in pre-bronchodilator FEV1 from baseline to Week 12 be tested at the same two-sided 0.049 level.

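### The protocol's 99% power for Week 12 FEV1 is that of the FEV1 test taken alone; under the fixed testing sequence it is about 89% at the planning assumptions (minor)

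*Protocol*

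**What the plan says.** Protocol section 9.2 gives power separately for two primary endpoints, each at two-sided 0.049. For the exacerbation rate it states 90% power for a 25% reduction, with 462 patients per arm. For Week 12 FEV1 it states that "the study will have 99% power to detect a 0.1L improvement", "assuming a common standard deviation of 0.35 and 5% of patients with missing data".

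Protocol section 9.4.1.1 then orders the tests: "A sequential testing procedure will be used for testing the two primary endpoints in the following order", with the exacerbation rate first and Week 12 FEV1 second. FEV1 becomes testable "Only upon rejection of the null hypothesis for the annualized rate of moderate and severe COPD exacerbations". Both tests use the same level, because "an administrative penalty of 0.001 will be taken from the significance level used at final analysis and thus two-sided 0.049 will be used".

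Neither document gives the power of the sequence as a whole. The SAP (sections 1.2.1, 1.3, 2.1.3 and 2.4.4.3) has one primary endpoint, the exacerbation rate, and bases the sample size on it alone. It lists Week 12 FEV1 as the first key secondary endpoint, tests it directly after the primary at 0.049, and states no FEV1 power.

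**The concern.** A formal FEV1 claim needs two rejections, and the first has about 90% power. At the assumptions in section 9.2 the chance of reaching the claim cannot be higher than that. The 99% is nevertheless given as what the study will have, with no note that it presumes the first test has already succeeded.

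Read as written, the figure puts the risk of missing on FEV1 at about 1%. Under the protocol's own testing order that risk is about 11%. It also depends on the exacerbation effect, which the FEV1 sentence does not mention. The protocol treats FEV1 as one of two primary endpoints and says the sample size rests on power for both, so a reader of 9.2 could take the second as nearly assured.

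**Working it through.** **Inputs** (all from protocol 9.2 and 9.4.1.1): 462 per arm; two-sided alpha 0.049, critical value 1.9686; placebo rate 1.5 per year, dupilumab rate 1.125 (rate ratio 0.75), dispersion 1, mean follow-up 0.95 year; FEV1 difference 0.1 L, SD 0.35 (unit taken as litres), 5% missing, so 462 × 0.95 = 438.9 per arm. Normal approximations are used throughout, ignoring the negligible opposite tail.

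**1. FEV1 test taken alone**

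- Standard error = 0.35 × √(2/438.9) = 0.02363
- Standardised effect = 0.1/0.02363 = 4.233
- Power = Φ(4.233 − 1.969) = Φ(2.264) = **98.8%**

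This reproduces the stated 99%.

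**2. Exacerbation test (the gate)**, Wald test on the log rate ratio:

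- Variance = [1/(1.5 × 0.95) + 1/(1.125 × 0.95) + 2 × 1]/462 = (0.7018 + 0.9357 + 2)/462 = 0.007873
- Standard error = 0.08873
- Standardised effect = |ln 0.75|/0.08873 = 0.2877/0.08873 = 3.242
- Power = Φ(3.242 − 1.969) = Φ(1.274) = **89.9%**

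This reproduces the stated 90%. With a pooled-rate null variance the result is 90.0%.

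**3. FEV1 under the sequence.** FEV1 is rejected only if both tests reject.

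- Independent tests: 0.8986 × 0.9882 = **88.8%**
- Lower bound for any dependence: 0.8986 + 0.9882 − 1 = **88.7%**
- Upper bound: the gate itself, **89.9%**
- Bivariate normal statistics with correlation from 0.1 to 0.8: 88.9% to 89.7%

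The gap to the stated 99% is about 9 to 10 points, and the unknown correlation hardly affects it.

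**4. Sensitivity to the true exacerbation reduction** (assumed values; other inputs unchanged; independent tests)

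| True reduction | Gate opens | FEV1 power under the sequence |
|---|---|---|
| 18% | 61.5% | 60.8% |
| 20% | 71.5% | 70.6% |
| 25% (planned) | 89.9% | 88.8% |
| 30% | 97.8% | 96.7% |
| 35% | 99.7% | 98.6% |

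The lower rows are worth showing because protocol section 2.2 itself reports an 18% to 20% reduction for an anti-IL-5 antibody in patients with high eosinophils. That is another drug, so it does not forecast this one. The calculation makes no allowance for stopping at the non-binding futility look.

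**The case against.** The strongest reply is that nothing was miscalculated. Section 9.2 works endpoint by endpoint, giving each its own effect size, variability and alpha, and never claims a joint power. The gate is openly stated in 9.4.1.1, and a reader who puts 90% and 99% beside a fixed sequence can see the cap. Quoting the power of each test separately is common. All of this stands: the 99% is right for what it measures, and what is missing is a label and a second figure.

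The SAP also reduces the weight of the point. It moves FEV1 to the first key secondary position, declares the study positive on the exacerbation endpoint alone, and drops the FEV1 power. SAP section 1.5 lists changes relative to protocol amendment 7 and does not mention this move, so the SAP may have been written against other protocol text than that supplied. The documents do not settle this. The gate remains in the SAP, so the protocol figure is still unreconciled.

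Three stronger readings are tempting, and the documents support none of them.

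- **That 99% is an arithmetic error.** It reproduces.
- **That FEV1 power can never exceed about 90%.** That ceiling belongs to the planning assumptions. A 30% reduction would give about 97%.
- **That the synopsis contradicts the 5% missing data by giving an "estimated total of 462 evaluable patients per intervention group".** The efficacy population is all randomised patients (protocol 9.3). The exacerbation model uses partial follow-up through its offset, and the FEV1 repeated-measures model uses values from visits up to Week 12. A patient without a Week 12 value can therefore still contribute to both analyses, and the FEV1 power already allows for the 5%.

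**Conclusion.** The point holds as a minor reporting matter. The 99% in protocol 9.2 is the power of the FEV1 test on its own, and the prespecified sequence does not deliver it. At the protocol's own assumptions (25% reduction, placebo rate 1.5, dispersion 1, 0.95 year of follow-up, 0.1 L difference, SD 0.35, 5% missing) the figure under the sequence is about 89%, whatever the dependence between the tests. Away from those assumptions it follows the exacerbation effect in both directions.

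A reader might infer that the trial is underpowered for FEV1 or that its error control fails. Neither follows. The FEV1 test is well powered once it is reached, and the fixed sequence is a valid way to hold the level at 0.049.

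**What to change.** In protocol 9.2, replace the FEV1 power statement with wording to this effect: *about 99% power for the FEV1 test taken alone; about 89% probability of rejecting both nulls under the fixed testing sequence and the stated assumptions.* Optionally add that the second figure is about 71% at a true exacerbation reduction of 20% and about 97% at 30%.

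The SAP needs no correction on this point, since it states no FEV1 power. If one is added there, it should carry the same label. The synopsis participant count can stay as it is.

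The cost is one sentence and a less favourable headline figure. Sample size, alpha, test order and analysis are unchanged.
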